9.4.5. Open-Label Efficacy Outcomes and Analyses

Efficacy data (ESS, PGIC, IHSS, FOSQ-10, VAS, Sleep diary, and WPAI:SHP) is collected across the study; refer to the schedule of events for further information on the collection schedule for these outcomes. All data will be summarized (per similar derivations as indicated in the above corresponding endpoint sections) using descriptive statistics by time point according to baseline medication group using the SAF.

At each time point, the change from the beginning of the OTTP or screening, as appropriate, will also be reported for ESS, IHSS, FOSQ-10, VAS (last week of screening), TST (last week of screening), and WPAI:SHP.

Efficacy data will be plotted in a figure by time point across the study according to baseline medication group and overall SAF across the study. Additionally, figures by time point through the DBRW by randomized treatment group will be provided for ESS and IHSS.

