6.14.2. Patient Global Impression of Change

The PGIC is a 7-point Likert-type rating scale and a widely used assessment to assess efficacy in clinical drug trials. Subjects will rate the change in their condition since a specified time point on a 7-point scale ranging from 1 (very much improved) to 7 (very much worse) ([Appendix 8](#) and [Appendix 9](#)).

The PGIC will be implemented at each clinic visit during the Open-label Treatment Titration and Optimization Period (starting at Week 1), during the End of Titration Visit, at the End of Stable Dose Visit, at the End of Double-blind Randomized Withdrawal Visit, and at clinic visits during the Open-label Safety Extension Period (Weeks 2, 6, 14, and the End of Open-label Extension Visit/Early Termination).

At all study visits except the End of Double-blind Randomized Withdrawal Visit, subjects will rate their change in condition compared to the Baseline Visit ([Appendix 8](#)). At the End of Double-blind Randomized Withdrawal Visit, subjects will rate their change in condition compared to the previous clinic visit (the End of Stable Dose Visit) ([Appendix 9](#)).

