9.9.1.4. Exploratory Efficacy Analyses

Analyses of all continuous exploratory endpoints (VAS [mean of daily assessments], TST, and WPAI:SHP) will be performed using ANCOVA, similarly to the primary endpoint.

Efficacy and quality of life data collected in the open-label periods will be summarized using descriptive statistics for each timepoint by prescreening group. The change from baseline (beginning of the Open-label Treatment Titration and Optimization Period) will also be reported for ESS, FOSQ-10, VAS, TST, and WPAI:SHP.

Outcomes relating to work productivity and activity impairment will further be defined in the SAP.

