7.1. General Methods

Analyses and summary outputs will be generated using SAS® version 9.4 (or higher). Categorical variables will be presented using counts and percentages. Unless otherwise specified, continuous data will be summarized using descriptive statistics comprising of the number of subjects with data to be summarized (n), mean, SD, median, minimum (Min) and maximum (Max).

For quantitative measurements, change from baseline will be calculated as:

- Change from baseline = Test value at visit X – baseline value

Unless otherwise specified, analyses based on mITT or DBRW SAF that intends to compare the two randomized treatment groups or to summarize the data during DBRW will be presented by randomized treatment group. In general, other analyses will be summarized by baseline medication groups. Summaries by baseline medication group (as defined in the electronic database) and baseline medication subgroup of efficacy analyses will be combined if there are too few subjects in any group.

- Group 1 and Group 2 will be combined if there are less than 10 subjects in either group and outputs will be summarized by Group 1 or 2 vs Group 3 vs Group 4.
- If the combined total of Group 1 and Group 2 is less than 10, then Groups 1, 2, and 3 will be combined. In this case, outputs will be summarized by Group 1 or 2 or 3 (Receiving Baseline IH Medication) vs Group 4 (Treatment Naïve).

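### SAP 9.4.5 pools placebo and JZP-258 subjects at End of DBRW in its across-study efficacy summaries, and mixes two PGIc reference points in one series

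*SAP*

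**What the plan says.** SAP 9.4.5 names seven sources of efficacy data (ESS, PGIc, IHSS, FOSQ-10, VAS, sleep diary, WPAI:SHP). It says that this information "is collected across the study; refer to the schedule of events for further information on the collection schedule for these outcomes", and that all of it is summarised "using descriptive statistics by time point according to baseline medication group using the SAF". For the figures it says: "Efficacy data will be plotted in a figure by time point across the study according to baseline medication group and overall SAF across the study". It then adds that "figures by time point through the DBRW by randomized treatment group will be provided for ESS and IHSS". Change from the start of titration (or from screening) is also reported at each time point for ESS, IHSS, FOSQ-10, VAS, TST and WPAI:SHP.

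SAP 7.1 reserves display by randomised arm for "analyses based on mITT or DBRW SAF that intends to compare the two randomized treatment groups or to summarize the data during DBRW". For everything else the default is: "In general, other analyses will be summarized by baseline medication groups".

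The protocol is narrower. Section 9.9.1.4 reads: "Efficacy and quality of life data collected in the open-label periods will be summarized using descriptive statistics". Section 9.1 has DBRW results summarised by treatment group. On PGIc, protocol 6.14.2 says: "At the End of Double-blind Randomized Withdrawal Visit, subjects will rate their change in condition compared to the previous clinic visit", that visit being End of Stable Dose. At all other visits PGIc is rated against Baseline.

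**The concern.** The overall SAF is everyone who took at least one dose (SAP 6), and randomisation is 1:1. During DBRW, about half of the subjects in any baseline medication group are therefore expected to be on placebo. A summary by medication group alone averages the two arms at that visit. A reader following the plotted line would see sleepiness rise at End of DBRW and fall again in the extension, and could take it for loss of benefit on JZP-258 when it comes from the placebo subjects.

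PGIc has a second problem at the same visit. The question changes, so a rating there is on a different footing from the ratings before and after it, even within one arm.

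At stake is the correct reading of descriptive tables and figures intended for the study report. No hypothesis test depends on them.

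**Working it through.** **1. Does the text bring placebo data into these outputs?**
- Analysis set: overall SAF, all dosed subjects (SAP 6). Nothing in 9.4.5 removes placebo subjects or DBRW visits.
- Time points: End of DBRW is a defined analysis visit for ESS, IHSS, PGIc, FOSQ-10 and WPAI:SHP (SAP 7.2.3, Table 3). VAS and diary are collected daily through DBRW (protocol 6.8, 6.14.7, 6.14.8).
- Grouping: the by-arm rule in SAP 7.1 covers mITT and DBRW SAF analyses. An overall-SAF output falls under the medication-group default.
- Contrast within the SAP: across-study adverse event summaries exclude DBRW events in subjects randomised to placebo (10.2), and duration of exposure to JZP-258 excludes placebo time (10.1.1). Efficacy has no matching exclusion.
- SAP 7.6, the list of changes from the protocol, does not mention the wider scope.

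**2. Confirm the design inputs.** SAP 5.4 gives a difference of 3.5, SD 5.5, 56 per arm, two-sided 0.05, and one interim look at 60% information.
- Standardised effect = 3.5 / (5.5 × √(2/56)) = 3.5 / 1.039 = 3.367.
- Fixed design: Φ(3.367 − 1.960) = 92.0%.
- Two-look Z test with the protocol's boundaries (0.0075 and 0.0476): power 91.84%, overall alpha 0.04995. The stated 91.8% reproduces.
- Enrolment: 112 / (1 − 0.20) = 140, as stated.

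**3. Displacement of the pooled ESS point.** Let p be the placebo share and D the placebo-minus-JZP-258 difference. Then:

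pooled mean = (1 − p) × JZP-258 mean + p × placebo mean = JZP-258 mean + p × D

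With D = 3.5:

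| Placebo share p | Above JZP-258 mean (p × 3.5) | Below placebo mean ((1 − p) × 3.5) |
|---|---|---|
| 0.4 | 1.40 | 2.10 |
| 0.5 | 1.75 | 1.75 |
| 0.6 | 2.10 | 1.40 |

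The 0.5 row is the planned allocation. The other two rows are an assumed range for imbalance within a medication group; the documents give no group sizes. The documents give no design difference for the other scales, but under 1:1 allocation each is displaced by half of its own arm difference.

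**4. PGIc.** Subjects not on Xyrem at entry can be randomised only if their End-of-SDP rating against Baseline is minimally, much or very much improved, which is category 3, 2 or 1 (protocol 4.3.3, Appendix 8). A JZP-258 subject whose condition then holds exactly steady should answer no change, category 4, at End of DBRW (Appendix 9). The recorded value moves by 4 − 3 = 1 to 4 − 1 = 3 categories with no clinical change. In the extension the reference returns to Baseline. Splitting by arm does not remove this.

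**5. Extent.** Titration, Stable Dose and extension visits are all on open-label JZP-258 (protocol 5.2), so only the DBRW point is mixed. After screening, VAS and diary are collected only in SDP and DBRW, so their across-study series ends on pooled data with no later open-label point.

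**The case against.** The best defence is that SAP 9.4.5 is headed as an open-label section, matches protocol 9.9.1.4 in purpose, and was never listed as a departure. SAP 9 also says that efficacy is presented primarily by randomised group on the mITT unless otherwise described. On that reading the DBRW comparison belongs to 9.1 to 9.4, and 9.4.5 covers only the open-label course. The table shells, which are not in these documents, may already do the right thing.

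This shows what may have been intended but does not settle the text. The body covers all data across the study, and its own by-arm figures through DBRW for ESS and IHSS show that DBRW is in scope. The SAP 9 default yields where something else is described, and 9.4.5 does describe something else.

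Other parts of the defence stand and limit the point:
- A reader might infer that the whole time course describes neither treatment. It does not: every point outside DBRW is on JZP-258.
- A reader might infer that only ESS and IHSS are shown by arm. That is true of time-course figures only. SAP 9.1 to 9.4 analyse every DBRW endpoint by arm, ESS also has a box plot by arm (9.1.1), and each primary and key secondary endpoint has a forest plot of the treatment difference (9.4.4).
- A reader might extend the reference-point problem to CGIc in this section. CGIc is not among the measures listed in 9.4.5, so no remedy is needed there.
- PGIc is not in the change-from-start list, and its change of reference is deliberate and documented. The problem is confined to its by-visit summary and figure.

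**Conclusion.** The point holds for one visit in descriptive output. Followed literally, SAP 9.4.5 gives an End-of-DBRW value (DBRW weeks for VAS and diary) that averages placebo and JZP-258, contrary to protocol 9.1 and 9.9.1.4. For ESS the displacement is 1.75 points, half the design effect, or 1.4 to 2.1 points if a medication group's placebo share is between 40% and 60%. This assumes that the design difference of 3.5 is realised and that the arms have equal mean ESS at End of SDP, as randomisation gives in expectation. The End-of-DBRW PGIc is also not comparable with the other visits in its series. The documents do not support any reading under which the primary or key secondary tests, alpha, power or sample size are affected. This is a minor correction.

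**What to change.** In SAP 9.4.5, do one of the following:
- restrict the baseline-medication-group and overall-SAF tables and figures to open-label visits, as protocol 9.9.1.4 has it; or
- keep the DBRW time points but show them by randomised arm for every listed measure.

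For VAS and sleep diary the second option keeps more information, since the first leaves only screening and SDP points.

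Under either option, take End-of-DBRW PGIc out of the Baseline-referenced by-visit series and present it separately, labelled as change since End of SDP. If any pooled DBRW display is retained, record it in SAP 7.6 as a change from the protocol.

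The cost is a few sentences of SAP text and the matching table and figure shells. No new data are needed.

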9.5. Efficacy and COVID-19 considerations

9.5.1. Alternative methods for efficacy assessment

The ESS, PGIC, IHSS, FOSQ-10, and WPAI:SHP are self-administered efficacy scales that would normally be completed on paper by the subject during the on-site visit. When a site visit is converted to a remote visit due to COVID-19, Jazz has instructed sites to have an appropriately delegated site staff read the scale instructions, questions, and possible responses (if applicable) verbatim to the subject. Subject answers are to be recorded on the form, along with the name of the site staff performing the assessment and the type of communication (telephone vs. video).

For the CGIC, the Investigator will conduct the interview via telephone (rather than face-to-face) in order to make the assessment.

VAS for sleep inertia and TST are entered by the subject into the remote device at home. All subjects were in possession of these devices prior to the onset of the public health emergency, no changes were made. At site visits, diary data is accessed via a remote portal by the site staff and reviewed with the subject. Therefore, this aspect of efficacy data collection and review of diary data remains essentially unchanged with remote visits.

9.5.2. Assessment of Efficacy due to COVID-19 considerations

Results will be primarily be presented combining efficacy data that is collected on-site and remotely. However, to ensure consistency in treatment effect, a subgroup analysis by on-site vs remote assessment will be performed for the primary endpoint and key secondary endpoints, as detailed in Section 7.5.

A listing of efficacy assessments that were collected remotely will be provided. This listing will contain the analysis visit name, date of assessment along with the name of the site staff performing the assessment, and the assessment total score.

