5.4. Power and Sample Size Considerations

A sample size of 56 subjects randomized per treatment group (total randomized sample size of 112 subjects) will provide 91.8% power to detect a difference of 3.5 points for the change in ESS between JZP-258 and placebo, from the end of the SDP to the end of the DBRW. This study was originally designed to include an optional IA for efficacy; thus, calculations were based on the following: a 2-sample Z test with a group-sequential design including one IA at 60% information fraction using a Lan-Demets alpha spending function that approximates the O'Brien-Fleming boundaries, a common standard deviation (SD) of 5.5 points in the change in ESS for both arms, and a 2-sided significance level of 0.05. Assuming a 20% dropout rate prior to randomization, approximately 140 subjects will be enrolled.

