7.5. Subgroups and Subgroup Analyses

Subgroup analyses will be conducted on the primary and key secondary efficacy endpoints for the following:

- Baseline Medication Group, if data are too sparse for at least one of the groups, then groups will be pooled (refer to section 7.1).
- JZP-258 stable dose regimen (e.g. once nightly vs twice nightly)
- Gender
- Region (North America vs Europe)
- High enrolling sites, based on the number randomized (Site XXX, Site XXX, vs all other)
- Baseline median BMI (kg/m^2) (\leq median vs $>$ median)
- Idiopathic Hypersomnia diagnosis (Long sleep vs without long sleep)
- With regard to COVID-19 considerations, Type of Visit (On-site vs Remote): On-site is defined as having both end SDP and end DBRW visits performed on site; Remote is defined as having at least one remote visit for either end SDP or end DBRW visit.

Should there be less than 20 subjects in any subgroup, then only summary statistics would be presented. The exception to this is the subgroup analysis for on-site vs remote; this subgroup analysis will be performed irrespective of subject numbers.

The output for estimating the treatment difference within subgroup will not be provided (least square [LS] means, standard error [SE], LS Mean Difference (95% confidence interval [CI]) or median difference (95% CI) and p-value) if the data are too sparse.

It should be noted that the study was not designed to detect treatment differences with high statistical power within any subgroups.

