9.4.4. Subgroup Analyses

Subgroup analyses for groups specified in section 7.5 will be performed for the primary and key secondary efficacy endpoint using mITT.

These subgroups will be analyzed similarly to the primary and key secondary efficacy analysis with the exception that for the Baseline Medication Group subgroup analyses, the Baseline Medication Group fixed effect will be excluded from the ANCOVA models. Normality assumptions will not be reassessed for subgroups. The corresponding parametric or nonparametric analysis used for the overall sample will be applied to each subgroup.

For each primary and key secondary efficacy endpoint, a forest plot summarizing the treatment difference and 95 % CI will be provided by each subgroup with sufficient sample size.

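### The on-site versus remote analysis is meant to show a consistent treatment effect, but the plan never estimates the difference between the two effects

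*SAP*

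**What the plan says.** SAP 9.5.1 explains that scales normally self-completed on paper at the site are read aloud to the subject by telephone or video when a visit is remote. SAP 9.5.2 combines both modes in the main results and adds a check: "to ensure consistency in treatment effect, a subgroup analysis by on-site vs remote assessment will be performed". It covers the primary and key secondary endpoints and refers to 7.5 for detail.

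SAP 7.5 counts a subject as remote if either the end-of-SDP or the end-of-DBRW visit was remote. It exempts this split from the 20-subject minimum: "this subgroup analysis will be performed irrespective of subject numbers". The within-subgroup output it lists is LS means, SE, the difference (or median difference) with 95% CI, and a p-value. It also cautions that "the study was not designed to detect treatment differences with high statistical power within any subgroups". SAP 7.4 makes subgroup p-values nominal.

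On method, SAP 9.4.4 says "These subgroups will be analyzed similarly to the primary and key secondary efficacy analysis". Whichever of the parametric or rank analyses was used overall is carried into each subgroup, and a forest plot is added for subgroups that are large enough. Neither document mentions an interaction term, an estimate of the difference between the on-site and remote effects, or a criterion for consistency.

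**The concern.** Whether the effect is consistent is a question about the difference between two treatment effects. Each planned p-value tests something else, namely that the effect in one subgroup is zero. A non-significant result in a small remote group can look like inconsistency when the effects are identical. Two significant results can look like agreement when the effects differ.

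This is the only planned comparison of treatment effects by mode of assessment, and it runs however few remote subjects there are. What is at stake is how the COVID-19 robustness statement is read, not the primary test.

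**Working it through.** **Inputs (SAP 5.4 unless noted).** 56 subjects per arm, 112 in total; two-sided 0.05; "91.8% power to detect a difference of 3.5 points for the change in ESS"; "a common standard deviation (SD) of 5.5 points in the change in ESS for both arms"; 1:1 randomization (SAP 5.1). The interim analysis was not performed (SAP 5.7.2). The number of remote subjects, r, is not in the documents, so a range is shown. Arms are assumed balanced within each subgroup.

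**The plan's own figure.** z = 3.5 / (5.5 × √(2/56)) = 3.5 / 1.039 = 3.367. Fixed-design power is Φ(3.367 − 1.960) = 92.0%. With O'Brien-Fleming-type Lan-DeMets spending and one look at 60% information, the nominal levels are 0.0076 and 0.0476 and the power is 91.8%. The stated figure is reproduced.

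**Power within a subgroup of n subjects.** SE = 5.5 × √(4/n) = 11/√n, so the noncentrality is 3.5√n/11 on n − 2 df (two-sample t-test).

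**Chance that exactly one subgroup has p<0.05.** The subgroups do not overlap, so P = p_on(1 − p_rem) + p_rem(1 − p_on). At r = 20: 0.855 × 0.729 + 0.271 × 0.145 = 0.663. If the remote effect is truly zero, p_rem = 0.05. At r = 20: 0.855 × 0.95 + 0.05 × 0.145 = 0.820.

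**The missing contrast.** SE = 11 × √(1/r + 1/(112 − r)). At r = 56 this is 2.079, and with t = 1.982 (108 df) the 95% CI half-width is 4.12 points.

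| Remote r | Power on-site | Power remote | One significant, equal effects | One significant, remote effect 0 | Contrast half-width | Interaction power, 3.5-point difference |
|---|---|---|---|---|---|---|
| 10 | 88.9% | 14.4% | 77.7% | 85.0% | 7.2 | 15.8% |
| 20 | 85.5% | 27.1% | 66.3% | 82.0% | 5.4 | 24.8% |
| 30 | 81.2% | 39.1% | 56.8% | 78.1% | 4.7 | 31.5% |
| 40 | 75.9% | 50.1% | 50.0% | 73.3% | 4.3 | 35.9% |
| 56 | 64.8% | 64.8% | 45.6% | 63.3% | 4.1 | 38.6% |

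Complete loss of the remote effect raises the rate of split p-values by only about 7 to 23 points. A simulation of the same t-tests (20,000 runs per setting) agrees closely and puts the largest gap at 22. With equal effects, an interaction test would raise a false alarm in 5% of trials at any split.

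**Sensitivity, equal effects.** With SD 4.5, as covariate adjustment might give, the split-p-value rate is 30% at r = 56 and 79% at r = 10. With a true effect of 5 and SD 5.5 it is 15% and 75%. The figure therefore depends strongly on effect and SD when the subgroups are similar in size, and hardly at all when the remote group is very small.

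**The case against.** The strongest objection is that the SAP contains no rule making consistency depend on each subgroup reaching p<0.05. It gives estimates, CIs and a forest plot, calls the p-values nominal, and warns about low subgroup power. A reader might infer from the table that the plan itself has a 46 to 78% error rate. The documents do not support that: the percentages describe a misreading that the output allows but does not prescribe. This objection stands, and the point is worded accordingly. What remains is that two CIs shown side by side are not a CI for their difference, which is the quantity that 9.5.2 asks about.

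Second, the interaction test is weak too. When the remote effect is zero, its rejection rate rises from 5% to between 16% and 39%. At 10 to 30 remote subjects that separates the two situations only about 3 to 5 points better than the p-value pattern does. The contrast half-width exceeds the 3.5-point design effect at every split shown. This also stands, so the case for the contrast is correct estimation, not detection.

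Third, one might invoke the clause in 7.5 that withholds treatment-difference output when data are too sparse. It gives no threshold and sits awkwardly with running this subgroup regardless of size, so it does not settle what will be shown.

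Finally, a reader might infer that the primary result is in doubt. It is not. Confirmatory testing is confined to ESS, PGIc and IHSS on the combined data, and nothing in that hierarchy depends on this subgroup display.

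**Conclusion.** The gap is real but small. The plan states a consistency question and provides only within-subgroup answers. At effect 3.5, SD 5.5 and N = 112, with equal true effects and balanced arms, comparing the two p-values would suggest disagreement in about 46% (56 remote) to 78% (10 remote) of trials. These figures are for ESS only and come from unadjusted t-tests, whereas the planned model is an ANCOVA. The documents give no planning assumptions for PGIc or IHSS. The lack of a contrast does not depend on any of these assumptions. No error rate or primary conclusion is affected.

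**What to change.** In SAP 9.5.2 and 9.4.4, add the following:

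- **ESS and IHSS:** one model on the full mITT set, being the primary ANCOVA plus visit type and treatment-by-visit-type. Report the difference between the on-site and remote treatment effects with its 95% CI.
- **If the rank branch of 9.1.1 is triggered:** keep the contrast on the original scale, because an interaction on ranks is not a difference in score points. One option is the difference between the two Hodges-Lehmann estimates with a bootstrap 95% CI.
- **PGIc:** the difference between the two risk differences, with the CI method named in advance (for example bootstrap or Newcombe-type).
- **Interpretation:** state that consistency is read from this contrast and its CI and not from within-subgroup p-values, and that a non-significant interaction does not show consistency.

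The cost is SAP wording and a few lines of programming, with no new data and no change to the primary analysis or alpha. The downside is a visibly wide ESS interval (half-width about 4.1 to 7.2 points at SD 5.5) and low interaction power (about 16 to 39% for a 3.5-point difference), which shows how little the trial can say on this question.
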